10. STATISTICAL DESIGN

The following is a brief description of the analyses to be described in this plan. If there are any changes from the analysis described below it will be detailed in the SAP and the Clinical Study Report (CSR). Any changes/additions to the analysis described in the SAP will also be detailed in the CSR.

10.1 GENERAL

Smith & Nephew's Global Biostatistics group will conduct the statistical analysis for this study. Unless otherwise stated, all significance tests and hypothesis testing will be two-sided, performed at the 5% significance level. Resulting p-values will be quoted and 95% two-sided confidence intervals will be generated where appropriate.

Where data summaries are specified, categorical and ordinal variables will be summarized with frequencies and percentages. Continuous variables will be summarized with the following summary statistics: number of observations, mean, median, standard deviation, minimum and maximum values. All analyses will be performed in SAS 9.4 (or later).

The handling of missing data will be detailed in the SAP.

10.2 ANALYSIS POPULATIONS

The following analysis populations will be used for this study:

- **Safety Population (SAF):** Including all subjects who enroll in the study and receive the study treatment. This population will be used for analysis of safety.
- **Modified Intention to Treat population (mITT):** following Intention to Treat principle including all subjects who are enrolled into the study and complete at least one post-baseline assessment. This population will be used for the primary analysis of the primary and secondary endpoints.

CONFIDENTIAL AND PROPRIETARY

This document contains information that is confidential and proprietary to Smith & Nephew PLC and Smith & Nephew, Inc. and is intended for use only by Smith & Nephew and its manufacturer. It shall not be reproduced or copied in whole or in part, nor shall the contents be disclosed by any means without prior written permission from Smith & Nephew, nor shall anyone make any use of it that is contrary to the expressed or implied wishes of Smith & Nephew.

| | |
|--|---|
| Study Protocol—Device |  |
| A Prospective, Multi-center, Post-Market Clinical Follow-Up Study to Evaluate the Safety and Effectiveness of ALLEVYN Gentle Border | Number: ALLEV.PMCF.2017.13 |
| | Version: 3.0 |
| | Date: 21 JUN 2019 |
| | Page: Page 49 of 90 |

- **Per-Protocol Population (PP):** including all subjects in the mITT, who have no significant protocol deviations and who meet the inclusion/exclusion criteria. This population will be used for a secondary analysis of the primary and secondary endpoints.

10.3 BASELINE DATA

Baseline data to be summarised includes: demographics, relevant medical history, wound type, wound location and duration of reference wound. Baseline data for all primary and secondary endpoints (clinical performance, dressing performance and patient reported outcomes) will be summarised along with the rest of the visits for each particular endpoint.

10.4 EFFICACY ANALYSIS

10.4.1 Analysis of Primary Endpoint

The primary endpoint for this study is the absolute reduction in wound area from baseline to end of study.

The reference wound area will be summarised at each dressing change assessment and study visit. The absolute reduction in the reference wound area from baseline to each post-baseline study visit will also be summarised.

The absolute reduction in area will be analysed as the dependent variable in a repeated measures ANCOVA model. As a minimum the models will contain a term for visit and the following terms will be added to the model using a stepwise selection procedure with an F-value to attain a significance level of 0.1: centre, wound type, BMI and baseline area. The estimate LSMean reduction in area from baseline to all study visits will be presented with the associated 95% confidence intervals, with the estimate for the end of study visit (day 28±3) being used for analysis of the primary endpoint.

If the assumptions of ANCOVA are not met then a non-parametric analysis will be considered.

The primary analysis analysis of this endpoint is to be carried out using the mITT population. The same analysis will be carried out on the PP population as a secondary analysis.

CONFIDENTIAL AND PROPRIETARY

This document contains information that is confidential and proprietary to Smith & Nephew PLC and Smith & Nephew, Inc. and is intended for use only by Smith & Nephew and its manufacturer. It shall not be reproduced or copied in whole or in part, nor shall the contents be disclosed by any means without prior written permission from Smith & Nephew, nor shall anyone make any use of it that is contrary to the expressed or implied wishes of Smith & Nephew.

| | |
|--|---|
| Study Protocol—Device |  |
| A Prospective, Multi-center, Post-Market Clinical Follow-Up Study to Evaluate the Safety and Effectiveness of ALLEVYN Gentle Border | Number: ALLEV.PMCF.2017.13 |
| | Version: 3.0 |
| | Date: 21 JUN 2019 |
| | Page: Page 50 of 90 |

10.4.2 Analysis of Secondary Endpoints

All secondary endpoints will be analysed using the mITT population as the primary analysis.

Wound Measurements

The reference wound volume and depth will be summarised at each dressing change assessment and study visit. The absolute reduction in the reference wound volume and depth from baseline to each visit will also be summarised.

The same analysis as the above repeated ANCOVA model is planned to be used to analyse absolute reduction in volume and depth (separately) from baseline to all post-baseline study visits. As well as the summaries of absolute reduction, the percentage reduction in area, volume and depth will also be summarised from baseline to all post-baseline study visits.

Cardiff Wound Impact Schedule (CWIS):

The CWIS consists of three domains: Social Life (CWIS-SL), Wellbeing (CWIS-WB), Physical Symptoms and Daily Living (CWIS-PSDL). For each domain a score from 0-100 is derived with higher scores being better.

Scores for each CWIS domain will be summarised at each study visit by wound type and overall. The increase in score from baseline to each study visit will also be summarised by wound type and overall.

A repeated measures ANCOVA model will be fit separately for each CWIS domain. In each case the domain score will be used as the dependent variable and as a minimum the model will contain a term for visit. The following extra terms will be added to the model using a stepwise selection procedure with an F-value to attain a significance level of 0.1: centre, wound type, BMI and baseline domain score. The estimate LSMean increase in domain score from baseline to all study visits will be presented with the associated 95% confidence intervals.

If the assumptions of ANCOVA are not met then a non-parametric analysis will be considered.

CONFIDENTIAL AND PROPRIETARY

This document contains information that is confidential and proprietary to Smith & Nephew PLC and Smith & Nephew, Inc. and is intended for use only by Smith & Nephew and its manufacturer. It shall not be reproduced or copied in whole or in part, nor shall the contents be disclosed by any means without prior written permission from Smith & Nephew, nor shall anyone make any use of it that is contrary to the expressed or implied wishes of Smith & Nephew.

| | |
|--|---|
| Study Protocol—Device |  |
| A Prospective, Multi-center, Post-Market Clinical Follow-Up Study to Evaluate the Safety and Effectiveness of ALLEVYN Gentle Border | Number: ALLEV.PMCF.2017.13 |
| | Version: 3.0 |
| | Date: 21 JUN 2019 |
| | Page: Page 51 of 90 |

Clinical and Dressing Performance

Performance endpoints to be summarised at all study visits and routine dressing changes by wound type and overall include:

- Reference wound healed (yes/no).
- Comfort during wear.
- Odour control – during wear and during dressing change.
- Showerproof qualities.
- Dressing retention, presence of bunching up and percentage dressing lift.
- Pain on application, during treatment and on dressing removal.
- Exudate type, amount and viscosity.
- Exudate management (fluid handling ability including leakage and percentage strikethrough).
- Dressing adherence to wound bed will be cross-tabulated by exudate level at previous dressing assessment.
- Dressing wear time (days) should be summarised for both wear time per subject i.e. take the average wear time for each subject and summarise that and also for the wear time of all dressings used in the study.
- Dressing change frequency will be summarised as the number of dressings per subject.
- Condition of surrounding skin will be summarised at all study visits and routine dressing changes. Also the condition of surrounding skin at each post-baseline study visit will be cross tabulated with condition of surrounding skin at baseline.
- Signs of clinical infection will be summarised at all study visits and routine dressing changes.

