This document contains information that is confidential and proprietary to Smith & Nephew PLC and Smith & Nephew, Inc. and is intended for use only by Smith & Nephew and its manufacturer. It shall not be reproduced or copied in whole or in part, nor shall the contents be disclosed by any means without prior written permission from Smith & Nephew, nor shall anyone make any use of it that is contrary to the expressed or implied wishes of Smith & Nephew.

| | |
|--|---|
| Study Protocol—Device |  |
| A Prospective, Multi-center, Post-Market Clinical Follow-Up Study to Evaluate the Safety and Effectiveness of ALLEVYN Gentle Border | Number: ALLEV.PMCF.2017.13 |
| | Version: 3.0 |
| | Date: 21 JUN 2019 |
| | Page: Page 24 of 90 |

Sizes and shapes used in this study

The study centers will be provided with ALLEVYN Gentle Border dressings based on the center specific needs. Figure 2 and table 2 show the different sizes and shapes available in the ALLEVYN Gentle Border range.

[figure not shown]

Figure 2: ALLEVYN Gentle Border Shapes

Table 2: ALLEVYN Gentle Border Size and Ordering Information

| S&N code | Dressing size | Carton |
|----------------------|----------------------|---------------|
| 66800269 | 7.5cm x 7.5cm | 10 |
| 66800270 | 10cm x 10cm | 10 |
| 66800900 | 10cm x 20cm | 10 |
| 66800264 | 10cm x 25cm | 10 |
| 66800265 | 10cm x 30cm | 10 |
| 66800272 | 12.5cm x 12.5cm | 10 |
| 66800506 (Heel) | 23cm x 23.2cm | 5 |
| 66800959 (Multisite) | 17.1cm x 17.9cm | 10 |
| 66800897 (Sacrum) | 16.8cm x 17.1cm | 6 |

AGB is designed to be worn for up to seven days. Subjects will have their dressings changed according to individual clinical need. The total duration of treatment with AGB will also depend on factors such as wound healing, topical wound treatments, or suitability of continued treatment with AGB. If the wound does not heal, the maximum study treatment period will be 4 weeks. In these

CONFIDENTIAL AND PROPRIETARY

This document contains information that is confidential and proprietary to Smith & Nephew PLC and Smith & Nephew, Inc. and is intended for use only by Smith & Nephew and its manufacturer. It shall not be reproduced or copied in whole or in part, nor shall the contents be disclosed by any means without prior written permission from Smith & Nephew, nor shall anyone make any use of it that is contrary to the expressed or implied wishes of Smith & Nephew.

| | |
|--|---|
| Study Protocol—Device |  |

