| A Prospective, Multi-center, Post-Market Clinical Follow-Up Study to Evaluate the Safety and Effectiveness of ALLEVYN Gentle Border | Number: ALLEV.PMCF.2017.13 |
| | Version: 3.0 |
| | Date: 21 JUN 2019 |
| | Page: Page 25 of 90 |

4 treatment weeks the dressing will be changed at minimum every week (each 7th day). Depending on the healing process, the number of AGB dressings used by each subject will differ.

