9. STUDY PROCEDURES

9.1 VISITS AND EXAMINATIONS

9.1.1 Summary

All subjects receive the ALLEVYN Gentle Border study device at visit 1 (Baseline, day 0). In total, all subjects need to perform 5 key study visits between week 1 and week 4, as shown in table 1. The visit schedule is based on the 7 days of maximum dressing wear time of ALLEVYN Gentle Border. The key visit date is counted from Baseline (day 0) and usually occurs on the same weekday in the following week. If a dressing change is required between the key visits the subject should come to an interim on-site visit (Routine Dressing Change Visit). A routine dressing change assessment will then be performed and documented in the Case Report Form. Then the subject

CONFIDENTIAL AND PROPRIETARY

This document contains information that is confidential and proprietary to Smith & Nephew PLC and Smith & Nephew, Inc. and is intended for use only by Smith & Nephew and its manufacturer. It shall not be reproduced or copied in whole or in part, nor shall the contents be disclosed by any means without prior written permission from Smith & Nephew, nor shall anyone make any use of it that is contrary to the expressed or implied wishes of Smith & Nephew.

| | |
|--|---|
| Study Protocol—Device |  |
| A Prospective, Multi-center, Post-Market Clinical Follow-Up Study to Evaluate the Safety and Effectiveness of ALLEVYN Gentle Border | Number: ALLEV.PMCF.2017.13 |
| | Version: 3.0 |
| | Date: 21 JUN 2019 |
| | Page: Page 35 of 90 |

continues with the next study key visit, counted from Baseline. If a subject is withdrawn from AGB treatment prior to key visit 5, this subject is still regarded as an active study participant. He/she should continue to come to the study key visit to follow-up with patients' safety up to visit 5.

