| 11. Record the total time that the subject spent at the visit (start to finish of wound care procedures). |
|---|

9.1.3 Study Visit 2 (day 7, ±3), Visit 3 (day 14, ±3), Visit 4 (day 21, ±3)

Visits 2 - 4 will be performed as on-site visits, so the subjects need to be present at each key study time point. These visits should take place every seventh (7) day. In case a dressing change is required before day 7, the instructions for a Routine Dressing Change Visit need to be followed (chapter 9.1.4).

Subjects who are already withdrawn from treatment and no longer require a dressing change shall be followed up on the study visits to collect safety information.

- | |
|---|
| 
 1. Question subjects regarding any changes in health or concomitant treatment. 2. Hand out the CWIS, Patient Assessment Scale and Pain Scale to the subject and allow sufficient time to complete it. 3. Photograph the dressing in situ prior to removal with the delivered digital camera. 4. Remove the old dressing and inspect the wound. Complete a wound assessment according to BWAT (see Section 9.2.4). 5. Assess the reason for dressing change, assess the ease of dressing removal and dressing leakage. 6. Record any debridement and the method of debridement, and take a photograph of the wound immediately prior to and following debridement. Note: Photographs are not necessary if the subject was withdrawn from treatment at a previous visit. 7. Redress the wound, if clinically indicated. 8. Record details of all dressings used (e.g. brand, size, etc.) as well as any treatment applied underneath the dressing. |
|---|

CONFIDENTIAL AND PROPRIETARY

This document contains information that is confidential and proprietary to Smith & Nephew PLC and Smith & Nephew, Inc. and is intended for use only by Smith & Nephew and its manufacturer. It shall not be reproduced or copied in whole or in part, nor shall the contents be disclosed by any means without prior written permission from Smith & Nephew, nor shall anyone make any use of it that is contrary to the expressed or implied wishes of Smith & Nephew.

| | |
|--|---|
| Study Protocol—Device |  |
| A Prospective, Multi-center, Post-Market Clinical Follow-Up Study to Evaluate the Safety and Effectiveness of ALLEVYN Gentle Border | Number: ALLEV.PMCF.2017.13 |
| | Version: 3.0 |
| | Date: 21 JUN 2019 |
| | Page: Page 37 of 90 |

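### Wear times cut short by a scheduled key visit are averaged as if complete, which can understate wear time, and the raw dressing count depends on time on treatment

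*Combined protocol and SAP*

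**What the plan says.** Wear time and change frequency are both secondary endpoints (section 8.2.2). For wear time, section 10.4.2 instructs the analyst to "take the average wear time for each subject and summarise that and also for the wear time of all dressings used in the study". For frequency it says: "Dressing change frequency will be summarised as the number of dressings per subject". The lead-in to that list is "Performance endpoints to be summarised at all study visits and routine dressing changes by wound type and overall include".

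Two rules govern when a dressing comes off:

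- **Need.** Section 6.1.1: "Subjects will have their dressings changed according to individual clinical need", with a maximum wear of 7 days.
- **Schedule.** Section 9.1.1: "The key visit date is counted from Baseline (day 0) and usually occurs on the same weekday in the following week". After an interim change the subject "continues with the next study key visit, counted from Baseline". Section 9.1.3 adds, for Visits 2 to 4, "These visits should take place every seventh (7) day". Each visit has a window of ±3 days. Removing the old dressing is a listed step at Visits 2–4 (section 9.1.3) and at the end of study visit (section 9.1.5).

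The reason for each change is recorded (sections 9.1.3 to 9.1.5 and 9.2.8), but the wear-time summary does not use it. Treatment may stop early, for example at wound closure (section 7.8.1). Duration of treatment is summarised as exposure in section 10.5, not as a denominator for the count.

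**The concern.** A dressing applied at an interim change on day 5 is removed at the day 7 visit after 2 days, whatever its condition. All that is known is that it would have lasted at least 2 days, yet the planned summary enters 2 days as its wear time. A visit held early in its window has the same effect on a dressing that was in step with the schedule. Dressings that reach the 7-day maximum are unaffected.

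Interim changes are foreseen in section 9.1.4, and eligible wounds are moderately to highly exuding, so such removals should not be rare. Separating key visits from routine changes does not isolate them, because a key-visit removal may be need-driven or visit-only.

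The count has a second problem. It has no time denominator, so a subject who leaves treatment early uses fewer dressings without the dressing having performed any better.

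At stake is how two named secondary endpoints are read in a study whose stated purpose is to support performance claims.

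**Working it through.** The plan states no wear-time or dressing-count figure, so there is none to reproduce. The 7-day maximum, the visits on days 7, 14, 21 and 28 and the removal at each visit come from the protocol. The distribution of need-driven wear is assumed throughout.

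**1. Fixed need, no distribution.** If every dressing needs changing after L days and visits are on schedule, each week uses ceil(7/L) dressings, so the reported mean is 7/ceil(7/L).

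| L (days) | Dressings in 28 days | Reported mean (days) | Error |
|---|---|---|---|
| 1 | 28 | 1.00 | 0 |
| 2 | 16 | 1.75 | −12.5% |
| 3 | 12 | 2.33 | −22% |
| 4 | 8 | 3.50 | −12.5% |
| 5 | 8 | 3.50 | −30% |
| 6 | 8 | 3.50 | −42% |
| 7 | 4 | 7.00 | 0 |

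Needs of 4, 5 and 6 days give the same mean and the same count, so the planned summaries cannot tell them apart.

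**2. Variable need, same distribution in every subject.** Need is gamma with mean 3, 4, 5 or 6 days and coefficient of variation (CV) 0.3 or 0.5, capped at 7. Removal is at the earlier of need and next key visit. The table shows the true capped mean against the planned pooled mean, and dressings in 28 days under the plan against need-only.

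| CV | Mean | True → planned (days) | Error | Dressings: plan vs need-only |
|---|---|---|---|---|
| 0.3 | 3 | 3.00 → 2.43 | −19% | 11.5 vs 9.9 |
| 0.3 | 4 | 3.99 → 3.07 | −23% | 9.1 vs 7.6 |
| 0.3 | 5 | 4.91 → 3.57 | −27% | 7.9 vs 6.2 |
| 0.3 | 6 | 5.64 → 4.00 | −29% | 7.0 vs 5.5 |
| 0.5 | 3 | 2.98 → 2.37 | −20% | 11.8 vs 10.0 |
| 0.5 | 4 | 3.88 → 2.95 | −24% | 9.5 vs 7.8 |
| 0.5 | 5 | 4.62 → 3.45 | −25% | 8.1 vs 6.6 |
| 0.5 | 6 | 5.20 → 3.92 | −25% | 7.2 vs 5.9 |

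The per-subject mean is 18–28% low, 33–46% of removals are visit-only, and the excess is 1.2–1.8 dressings at full time on treatment. Weibull need times (shape 1, 2 or 4; mean 3–8 days) give 19–29% low pooled and 15–29% low per subject.

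**3. Need varying between subjects** (between-subject CV 0.3 or 0.5, within-subject CV 0.2 or 0.3). Pooled wear is 15–26% low, the per-subject mean 19–25% low, with 1.2–1.7 extra dressings. At between-subject CV 0.5 and within-subject CV 0.2, true against planned per-subject means are 2.95 → 2.37, 3.86 → 3.03, 4.54 → 3.56 and 5.08 → 4.12. In these four cells:

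- Need-driven removals alone give 2.92, 3.83, 4.50 and 5.05. Over all simulated cells this summary is 0–8% low, because short wears complete more often.
- A pooled Kaplan–Meier mean that censors visit-only removals gives 2.36, 3.20, 3.92 and 4.44, which is 0.6–0.7 day below the subject-level mean.

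**4. Count with early exit at day 14**, against the need-only 28-day count. If 25% leave, the excess falls to between +0.2 and +0.6. If 40% leave, it lies between −0.6 and +0.1. If every dressing lasts 7 days and 25% leave, the mean count is 0.75 × 4 + 0.25 × 2 = 3.5, against 4.0. Changes per 7 days on treatment stay at 2.9 from 0% to 40% exit (need mean 3, CV 0.3).

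**The case against.** **The planned means are correct for days actually worn.** Read literally, section 10.4.2 asks for that, and the comparison with need-driven wear is brought in from outside. This stands as a matter of definition. But wear time is reported as dressing performance, and a figure partly set by the visit calendar does not measure that.

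**The percentages assume exact visit days.** The ±3-day window could absorb needed changes. If a key visit is held at the needed change whenever that falls within 1, 2 or 3 days of the nominal day, the pooled shortfall in the step 2 scenarios drops to about 8–21%, 1–10% or 0–3%. This also stands: the larger figures belong to a strict schedule. Full absorption cannot be relied on, because section 9.1.3 sends a change needed before day 7 to a routine visit. Section 9.1.5 asks for the visit to match the normal dressing change only at end of study, and it assumes a 7-day rhythm that interim changes break.

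**More detail may exist elsewhere.** Section 10 calls itself brief and refers to the SAP, the list in section 10.4.2 is open-ended, and treatment duration is summarised. No separate wear-time rule appears in the documents, though, and an overall exposure summary does not adjust the count subject by subject.

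**The consequence is small.** Agreed: both endpoints are descriptive, with no comparator, test or threshold.

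**Conclusion.** The concern holds, at low priority. The planned averages mix wear times cut short by a visit with complete ones, so reported wear time can be biased down. Under the assumed need times and exact visit days the shortfall is about 15–29%. It shrinks as visits absorb needed changes and is near zero when they coincide. The true size cannot be known from the documents. The raw count mixes visit-only changes with time on treatment, so the direction of its net bias is not guaranteed. The wear-time error runs against the product, and the primary analysis is unaffected.

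**What to change.** Keep the planned summaries and add to the SAP:

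- Wear time by recorded reason for change, per subject and pooled, with removals made only because of a key visit or end of study shown separately. Note that the need-driven group remains slightly low (0–8% per subject in the simulations).
- A rule, built on the reason-for-change categories, for when a key-visit removal counts as need-driven.
- Dressing changes per 7 days on treatment beside the raw count, also by reason. The rate removes the dependence on time on treatment but not the visit-only changes.

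A Kaplan–Meier summary that censors visit-only removals is optional. If used, it should be supplementary, labelled as a per-dressing estimate and allow for clustering within subject. It should not replace the per-subject average, for the reason shown in step 3.

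The cost is SAP wording and a little programming, since reason for change and duration of treatment are already recorded. The documents do not show the reason categories. If none means scheduled visit only, one CRF option is needed. No visit, procedure or primary analysis changes.
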